In this study, the aim is to prospectively implement our NLP substance misuse classifier to examine its effectiveness in augmenting current practice that features physician referrals in hospitalized adult patients at Rush University Medical Center (RUMC).

STAFF

All work involving patient data will be performed at Rush and Rush staff will gain access to the Rush servers with approved credentialing and authentication by Rush IT. No data will be accessible to external investigators without a fully executed data use agreement and/or IRB approval / SMART IRB reliance agreement.

TRIAL SETTING AND PARTICIPANTS

This pragmatic, quasi-experimental (pre-post) study will be implemented at Rush University Medical Center across the surgical and medical wards. The study will target all adult hospitalized patients over a 24-month period (12 months of manual screen and 12 months under implementation of the NLP tool) and an additional 6-month follow-up for secondary outcomes. Currently, SUIT performs screening for patients identified from physician referrals between 8am-6pm and Monday-Friday and uses Epic (Epic Systems Corporation, Verona, Wisconsin) EHR.

METHODS AND MATERIAL

Overview:

We will use a quasi-experimental, interrupted time series (ITS) design to evaluate the longitudinal effects of the automated screening classifier compared to the manual screen approach at Rush. ITS offers several advantages in making use of our longitudinal data. Our analysis will model the trend in the outcome before the implementation of the automated screen, the change in the outcome that can be attributed to the automated screen and the difference between the slopes in the pre-period versus post-period. It is anticipated that no other interventions that may impact the study outcome will occur during the study period.

A comparison cohort from the manual screen period will extend from August 1, 2022 to July 31st, 2024. The day of switching on the automated screen will mark the start of the intervention period on August 1, 2023 and extend through July 31, 2024. This provides a 30-month total study period (12 months manual screening, and 12 months automated screen, and 6 months additional follow-up for secondary outcomes).

Approach:

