The primary outcome is the count of patients who received the composite outcome of any of the following: naloxone dispensing [prescription, free kit from clinic, or order for home kit], medication assisted treatment [buprenorphine, methadone, naltrexone, acamprosate, gabapentin, disulfiram], addiction consult, referral to outpatient treatment, brief intervention/motivational interviewing for substance misuse. Each component will be indicated separately in the flowsheet for the encounter, along with the type of SUIT team involvement: formal consultation, curbside consultation, or supporting other service. The design is an interrupted time-series prospective observational study. [Time Frame: 30 months]

The secondary outcome is all-cause re-hospitalizations following 6-months from the Index hospital encounter. We will compare healthcare utilization outcomes in all patients between manual screen period and automated screen period controlling for all patient demographic and clinical characteristics. [Time Frame: 24 months of evaluation with 6 months follow-up for rehospitalization] Further exploratory outcomes include analyzing each component of the primary outcome separately: naloxone dispensing, medication assisted treatment, addiction consult, referral to outpatient treatment, brief intervention/motivational interviewing for substance misuse.

Analysis Plan:

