ACFs and partial ACFs will be used to determine the orders of autoregression (AR) or moving average (MA) that will correct for the remaining autocorrelation. We hypothesize that the intervention will promote a step change (binary indicator for a level shift when intervention begins) and possibly a ramp effect (variable takes the value of 0 before the intervention and increases by 1 for each month following the beginning of the intervention). Fit statistics (AIC, BIC) and residual analysis (Ljung-Box test for white noise) will be used to identify a parsimonious and appropriate model based on AR/MA orders, differencing assumptions, and parameters for intervention impact (step, pulse, or ramp).

Specific aim 2: The number of hospitalizations in the 6 months following the index encounter will be regressed on time period of index hospitalization (manual screen or automated screen) and patient demographic and clinical characteristics using mixed-effects Poisson regression models. GLMMs with appropriate link and distributions specified will consider other follow-up utilization outcomes (e.g., costs, any encounter).

Power analysis:

A simulation study was designed to examine potential step effects in a non-inferiority design. In 2020, there were 95 ± 10 addiction consults per month and an autocorrelation AR(1) of $\phi=0.4$. Additionally, we performed silent testing of the automated screener in 2020 where it detected ~ 70 additional cases of substance misuse per month that did not receive consults by the usual care approach. We propose that a non-inferiority margin of 15 consults is acceptable and a step effect of 20 is a feasible goal with the implementation of automated screening. Assuming a similar consult rate of 95 ± 10 per month in this study's pre-period (July 2022-June 2023) and $\phi=0.4$, we have 80% power to detect a step effect of +20, resulting in 115 ± 10 consults per month in the post-period (July 2023-June 2024).

Data Elements:

RUSH EHR

The following electronic health record data elements will be included in the data sets used for analysis. Most data will be obtained through direct extraction of EPIC; however, some data may be computed from EHR data and obtained through the Rush Clinical Research Analytics team or transformed from EHR data by the research team (NLP mapped concepts from the text):

- MRN
- Address with Geocoding
- Census Tract Identifiers
- Encounter ID and type

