- Date / time Stamps for all EHR data (e.g. admission / discharge, procedures, assessments, notes, etc. (time-shifted for final analysis))
- De-identified concept unique identifiers (CUIs) from all clinical documentation in the EHR (process described below)
- Nursing assessments and flowsheets including AUDIT, DAST, and universal screens
- Clinical / nursing assessments, flowsheets, documentation including SUIT data
- Insurance status
- Vital signs (including respirator settings and data)
- Co-morbidities
- ICD and CPT codes

- Cost, charges and reimbursement data associated with all the CPT, ICD9/10, and medications
- patient location
- laboratory results
- radiological orders
- interventional orders including addiction consult orders
- diagnostic test orders
- medication ordered and administered
- sex
- age
- race / ethnicity
- primary and secondary diagnoses
- date of admission
- date of discharge
- dates related to notes, assessments, procedures, orders, reports, vitals, observations, events, diagnoses, etc.
- discharge disposition
- adverse events during hospitalization, defined as Rapid Response Team activations, ICU transfer, cardiac arrest, or mortality
- OR procedures
- OR admission and discharge

DURATION

It is expected that participant enrollment will begin by January 1, 2018 and that human subjects activities will be complete by June 30, 2024. In this pre-post design, a manual screen cohort of patients will provide the comparison. The automated screen period will run prospectively on hospitalized patients over a 12-month period between July 1, 2023 and June 30, 2024. During these study periods, all patient data (for patients ages 18 and above) will be collected.

LOCATION

Research will be conducted at Rush University Medical Center by study staff from Rush. Staff from ITM Loyola and UW-Madison may consult on analyses. All data will be housed at Rush and analyzed on our systems. PHI will not be released outside of Rush.

TYPE AND NUMBER OF SUBJECTS

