EHR data for adult (ages 18 and above) patients will be collected. The target study population is adult (ages 18 and above)- male or female – that were identified by the manual or automated screening for substance misuse at Rush University Medical Center. Additionally, patients meeting only the age criteria within the specified time-frame for the study may be included for analyses regardless of potential of or screening for substance misuse. Investigators at Rush University anticipate approximately 57,800 RUMC patients will be included in the analysis, based on preparatory research planning.

POTENTIAL RISKS & BENEFITS

The main risk to subjects is breach of confidentiality. All data is maintained electronically and stored on password-protected computers using secured servers with limited access maintained at Rush University Medical Center. For analysis, Rush will access a delimited file containing patient notes and then process the data, load the model, and make a prediction for each patient. The software will generate output in the

form of a delimited file linking each patient's unique identifier (such as MRN) to a prediction about the patient's alcohol, opioid, non-opioid, and polysubstance use statuses. All these activities will be performed locally within Rush's HIPAA-secure servers.

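### Aim 2's all-patient rehospitalization comparison is so diluted that plausible screener effects cannot be told from zero or from calendar drift

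*Combined protocol and SAP*

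**What the plan says.** Study Outcomes defines the endpoint: "The secondary outcome is all-cause re-hospitalizations following 6-months from the Index hospital encounter". The same paragraph sets the population: "We will compare healthcare utilization outcomes in all patients between manual screen period and automated screen period", with adjustment for demographic and clinical characteristics. The Analysis Plan, under Specific aim 2, gives the model: "The number of hospitalizations in the 6 months following the index encounter will be regressed on time period of index hospitalization", plus patient covariates, in a mixed-effects Poisson regression. No calendar-time term is named for this model. No baseline rate, detectable effect or power is given for this outcome; the Power analysis section covers consults only.

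Type and Number of Subjects expects that "approximately 57,800 RUMC patients will be included in the analysis". The same section describes the target population as patients found by the manual or the automated screen, and adds that patients who meet only the age criterion can also be analysed. That is not the same population as in Study Outcomes.

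**The concern.** Automated screening can lower rehospitalization only through patients whose care it changes. If these are a small share of all inpatients, the effect on the all-patient rate is diluted to near zero, while everyone else contributes noise and any change in case mix or practice between the two years. A null could then be reported as no effect on rehospitalization when a worthwhile benefit would have been missed. A significant difference could be credited to the screener when it reflects the calendar.

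The unreconciled population statement adds a second risk. Restricting to each period's own screen-positives would look like the natural repair, but manual screening stops when the automated screener starts (section on clinical decision support). Those cohorts would be selected by different instruments.

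**Working it through.** **Plan's own figure.** There is none to reproduce for aim 2. The 80% in Power analysis concerns a step in consults and does not bear on this point.

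**Inputs from the documents.**
- About 57,800 patients (Type and Number of Subjects).
- Period lengths: "12 months of manual screen and 12 months under implementation of the NLP tool" (Trial Setting and Participants).
- Baseline: "In 2020, there were 95 ± 10 addiction consults per month" (Power analysis).
- Planned step of 20 consults per month, and about 70 additional cases per month in silent testing (Power analysis).
- Misuse prevalence up to 25% (Scientific Review).

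**Assumptions.** Even split over 24 months, one index stay per patient, two-sided 5% test, r = 0.2, 0.4 or 0.8 readmissions per patient in 6 months, and a base rate in reached patients equal to (k = 1) or double (k = 2) the overall rate.

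**Share reached.** 57,800/24 = 2,408 per month. 20/2,408 = 0.83%; 70/2,408 = 2.9%.

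**Precision.** 28,900 per period. SE(log rate ratio) = sqrt(2/(28,900 r)) = 0.0186, 0.0132, 0.0093. The 95% half-widths (1.96 SE) are 3.6%, 2.6% and 1.8%.

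**All-patient power.** Fall f = share × k × reduction; z = |ln(1 − f)|/SE; power = Φ(z − 1.96) + Φ(−z − 1.96). Example: 70 per month, k = 2, 30% reduction, r = 0.4 gives f = 0.0291 × 2 × 0.3 = 0.0174, z = 1.34, power 27%.

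| Reached per month | Reduction in reached | k | Fall in all-patient rate | Power at r = 0.2 / 0.4 / 0.8 |
|---|---|---|---|---|
| 20 | 30% | 1 | 0.25% | 5 / 5 / 6% |
| 20 | 30% | 2 | 0.50% | 6 / 7 / 8% |
| 20 | 100% | 2 | 1.7% | 15 / 25 / 44% |
| 70 | 30% | 1 | 0.87% | 8 / 10 / 16% |
| 70 | 30% | 2 | 1.7% | 16 / 27 / 47% |
| 70 | 50% | 2 | 2.9% | 35 / 61 / 89% |
| 70 | 100% | 2 | 5.8% | 90 / >99 / >99% |

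Overdispersion lowers these. With a dispersion factor of 2, the 61% becomes 35%.

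**Drift.** Suppose the proportion with any rehospitalization moves by 1 point for reasons unrelated to screening. From 20% to 19%, SE = sqrt(2 × 0.195 × 0.805/28,900) = 0.0033, z = 3.03, and the chance of significance is 86%. From 25% to 24%, SE = 0.0036, z = 2.79, and the chance is 80%.

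**If the count covers a longer window.** The Duration section says: "It is expected that participant enrollment will begin by January 1, 2018". Spread over January 2018 to June 2024 (78 months), 57,800 is 741 per month. The shares become 20/741 = 2.7% and 70/741 = 9.4%, but each 12-month period holds only about 8,892 patients (SE 0.0335, 0.0237, 0.0168). Power for a 30% reduction is then 6-16% at 20 per month and 14-94% at 70.

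**Common at-risk cohort.** Take 165 per month (95 + 70, assuming the classifier flags all of them) or 602 (25% of 2,408). That is 1,980 or 7,224 per period. Assume 0.4 or 0.8 readmissions per patient and that everyone reached is in the cohort. For a 30% reduction, f = (reached/cohort) × 0.3:

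| Cohort per month | Reached | f | Power at 0.4 / 0.8 |
|---|---|---|---|
| 165 | 20 | 3.6% | 11 / 18% |
| 165 | 70 | 12.7% | 77 / 97% |
| 602 | 20 | 1.0% | 7 / 8% |
| 602 | 70 | 3.5% | 27 / 48% |

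The lowest value, 7%, is 6% if only rejections in the direction of benefit are counted. Effect over SE rises by sqrt(2,408/(cohort × k)): 2.0- to 3.8-fold at equal base rates, 1.4- to 2.7-fold if the cohort's rate is double.

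**The case against.** A reader might infer that only 1-3% of patients can have their care changed. The documents do not support that as a ceiling. The 20 is a net change in consults, while the composite also counts naloxone, medication, referral and brief intervention. The manual screen is withdrawn, so gains and losses can offset inside a small net figure. Misuse prevalence may reach 25%. If care changed for all 25%, a 20% reduction at average risk would lower the all-patient rate by 5%, with 79% to over 99% power on the same formula.

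A reader might also infer that the comparison must come out null whatever the screener does. That is wrong: the table shows that large effects in the 70 at double base rate are detectable, and drift alone can produce significance.

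An all-patient comparison is also a legitimate estimand. It gives the population-level effect and avoids selection by a different screen in each period. The plan adjusts for measured characteristics and anticipates no competing interventions. This stands as a reason to keep the analysis. It does not supply a detectable effect, and covariate adjustment does not remove unmeasured calendar change.

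**Conclusion.** The concern holds as a matter of interpretability. On the plan's own consult and silent-test figures with an even 24-month split, a 30% reduction in those reached has about 5-8% power at 20 per month and 8-47% at 70. Only large effects in the 70 at double base rate do better (halving 35-89%, full prevention 90-100%). Plausible effects cannot be separated from zero or from drift, so neither a null nor a non-null result would say much about the screener.

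This rests on assumed readmission rates, plain Poisson variance and the even split. On the 78-month reading the 20-per-month result stays poor, but the 70-per-month result depends heavily on the base rate. It would be too strong to say that the secondary objective cannot be answered at all: reach beyond these net figures, or very large effects, would show. Because this is a secondary outcome and the repair is cheap, the change is advisable rather than essential.

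**What to change.** Reconcile the population statements in Study Outcomes and in Type and Number of Subjects, but not by using each period's own screen-positives. Add to aim 2 an analysis, preferably the main one, of index stays flagged by the same locked classifier and cut-off. Run it in both periods on early-admission notes, leaving out screening and SUIT documentation. Keep the all-patient comparison as supportive. Report the period effect in unflagged patients as a concurrent negative control: a similar effect there points to drift. State the detectable effect, and state that the all-patient estimate cannot exclude a benefit in patients with misuse.

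The cost is SAP text and a batch classifier run on manual-period notes. The 2020 silent testing and the concept identifiers listed under Data Elements suggest that this is feasible, though the documents do not say that those notes are already extracted. Fewer patients are analysed. Results apply to early-flagged patients and miss those flagged at later nightly runs. The restriction does not rescue the 20-per-month case (about 7-18% power for a 30% reduction, against about 27-97% at 70), and the report should say so.

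### The primary ARIMA analysis selects its model from 24 monthly points and states no alpha, interval or small-sample method; with ordinary likelihood intervals, non-inferiority is declared too easily

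*Combined protocol and SAP*

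**What the plan says.** Trial Setting and Participants gives the series length: "12 months of manual screen and 12 months under implementation of the NLP tool", so 24 monthly counts. Under Analysis Plan, Overall approach, ARIMA is the primary method for aim 1.

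Specific aim 1 leaves the model to be settled from those counts. A transformation and differencing (d = 1 is the named example) depend on how the series looks. AR and MA orders are read from autocorrelation plots after differencing. Then "Fit statistics (AIC, BIC) and residual analysis (Ljung-Box test for white noise) will be used to identify a parsimonious and appropriate model", and that choice also covers the differencing assumption and whether the effect is a step, pulse or ramp.

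Power analysis frames the question as non-inferiority: "a non-inferiority margin of 15 consults is acceptable and a step effect of 20 is a feasible goal". Its inputs are 2020 addiction consults, 95 ± 10 per month with first-order autocorrelation 0.4, and it concludes "we have 80% power to detect a step effect of +20".

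The documents do not state an alpha, sidedness, a confidence level, a rule linking the interval to the margin, an estimator, a reference distribution or any small-sample correction.

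**The concern.** AIC and BIC presuppose a likelihood fit, so the natural default is maximum likelihood with a normal-quantile interval. With 24 points and two to four regression terms, that fit underestimates both the autocorrelation and the variance. Choosing the order from the same points adds to the problem, because a parsimonious model with too little autocorrelation will often pass the checks.

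Both effects make the interval too narrow. In a non-inferiority comparison that error favours the new method, since a loss of 15 per month is ruled out too readily. Manual screening is to end on the day the automated screen starts (section on clinical decision support with the classifier), so a mistaken finding of non-inferiority would endorse a replacement that had lost as many patients as the plan calls unacceptable.

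**Working it through.** **Inputs.** From the documents: 12 + 12 months, SD 10, φ = 0.4, margin 15, target step +20. Assumed because not stated: one-sided 2.5% (two-sided 95% interval), maximum likelihood, normal quantiles, SD 10 as the marginal SD, and consult figures standing in for the composite.

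**The plan's 80% first.** With autocorrelation inflation the effective SD is 10 × √(1.4/0.6) = 15.28, and the standard error of a difference of two 12-month means is 15.28 × √(2/12) = 6.24.

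- Test of step > 0 at +20: 20/6.24 − 1.96 = 1.25, power 89.4%. Ignoring autocorrelation it is 99.8%.
- Simulated AR(1) by maximum likelihood: 96.1% with a step only, 78.3% with step and ramp. A step model with first differencing and an MA(1) term, IMA(0,1,1), gives 81.9%.
- Non-inferiority at +20: (20 + 15)/6.24 − 1.96 = 3.65, power above 99.9%. Simulated undifferenced AR(1) models give 95–100%.

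So 80% can be reproduced, but as a test of step > 0 under some models and not as the non-inferiority test.

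**False non-inferiority.** The model is count = intercept + b × step (+ trend) (+ ramp) + u, with u following an AR(1) process. Non-inferiority is declared if b̂ − 1.96 × SE > −15. The error rate is how often this happens when b = −15.

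Fixed AR(1), no differencing, maximum likelihood, 40,000 simulated series:

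| Terms | False non-inferiority |
|---|---|
| step | 7.9% |
| trend + step | 8.0% |
| step + ramp | 9.0% |
| trend + step + ramp | 10.3% |

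Reading SD 10 as the innovation SD changes these to 8.0%, 8.1%, 9.1% and 10.4%. At a nominal one-sided 5% the rates are 11.3–14.0%.

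**Why.** For the step model the mean reported SE is 4.5, against a true SD of the estimate of 5.9. The nominal 1.96 is then worth 1.96 × 4.5/5.9 = 1.49 true standard errors, a one-sided tail of about 6.7%. Variation of the SE between series takes it to 7.9%. Coverage of the 95% interval is 84%. The mean estimate of φ is 0.25 (step), 0.19 (trend + step) and 0.10 (trend + step + ramp), against a true 0.4.

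**Dependence on φ.** Step only: 5.7% at φ = 0, 6.4% at 0.2, 9.9% at 0.6. Across models the rate at φ = 0 is about 6–7%, so the problem does not need autocorrelation.

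**Dependence on the model path** (exact likelihood, 8,000 series):

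| Path | False non-inferiority |
|---|---|
| d = 1, random-walk or AR(1) errors | 3.5–4.6% |
| d = 1, IMA(0,1,1) | 8.8–9.9% |
| d = 1, order chosen by AIC/BIC | 8.4–9.8% |
| d = 0, order chosen by AIC/BIC | 10.1–16.6% |
| d = 0, also choosing step or step + ramp | 14.5–14.8% |

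A standard state-space routine with default standard errors (600 series, Monte Carlo error about 1 point, some convergence failures) gave 5.3–6.0% for fixed AR(1), 9.3–9.8% with order selection at d = 0, and 3.7% at d = 1.

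**Remedies tested at φ = 0.4.** REML with z gives 5.3–5.9%, and REML with t gives 4.5–5.1%. REML with a parametric-bootstrap critical value gives about 2.3–3.6% across the step, trend + step and trend + step + ramp models, with the richest model at the upper end.

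**The case against.** A reader might infer that the plan carries an 8–10% error in place of its own 2.5%. The documents do not support that.

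- **No level is stated.** The 2.5%, the 95% interval and maximum likelihood are assumptions. AIC and BIC only imply a likelihood fit. This objection stands, but the inflation is also there at a nominal 5%.
- **8–10% describes one branch.** It belongs to a fixed, correctly specified AR(1) without differencing, while Overall approach and Specific aim 1 expect differencing and name d = 1. Some d = 1 models come close to nominal. This also stands, and the range has to be reported. The selection procedure in the quoted sentence is mostly worse than the fixed model, not better.
- **The inputs belong to another variable.** Study Outcomes defines the primary outcome as patients with any part of a five-part composite, and its SD and φ are not given. This stands. The φ = 0 result shows that the direction does not hinge on 0.4.
- **The autocorrelation plot.** The lag-1 value exceeds its limit in 19% of series only for residuals from the step-only model. It is 12% with a trend and about 5% with trend and ramp. In the raw series it is 74%, because the −15 shift itself produces autocorrelation. No single figure describes what the analyst will see.
- **A longer series.** Duration says "It is expected that participant enrollment will begin by January 1, 2018". A long pre-period would ease the problem, but no months before 2022 are assigned to the time series.

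Nor do the documents support reading this as an error in the 80% power figure, or as a forecast of a wrong result. At a true step of +20, the undifferenced AR(1) models conclude non-inferiority in 95–100% of series in any case. The defect matters when the truth lies near the margin.

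**Conclusion.** The concern holds in conditional form. The documented gap is that a non-inferiority conclusion will be drawn from 24 points, with a data-selected model and no stated alpha, interval, decision rule or small-sample method. If that gap is filled by the usual likelihood fit and a 95% normal interval, false non-inferiority at a true step of −15 is about 8–10% for a fixed undifferenced AR(1). It runs from about 3.5% to over 15% across the paths the plan leaves open. All specifications tried exceeded 2.5%, always in the direction that favours the automated screen. These sizes rest on Gaussian AR(1) monthly counts with the 2020 consult SD and φ. The direction is well supported; confidence in any one figure for the composite outcome is moderate at best.

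**What to change.** In the SAP, under Specific aim 1:

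1. State the one-sided alpha and the rule: non-inferiority is concluded if the lower confidence bound for the step exceeds −15.
2. Pre-specify the primary error structure (for example AR(1)) and the intervention terms, and do not select them from the same 24 points. This step alone is not enough, since the fixed AR(1) model still gives 8–10%.
3. Take the bound from a method calibrated for this series length. REML with a parametric-bootstrap critical value is one example; critical values from a simulation would serve the same purpose. REML with z or t alone leaves about 5–6%.
4. Keep the AIC/BIC-selected ARIMA, including d = 1, as a sensitivity analysis.

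The cost is SAP wording and a short simulation script, with no new data. The interval widens and apparent power falls. As an indication, at a true step of zero the step-only likelihood analysis appears to have 83.3% power for non-inferiority, while the closed form with the autocorrelation known gives 15/6.24 − 1.96 = 0.445, or 67.2%. Power for the calibrated analysis should be recomputed before the SAP is final.

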Overall approach: Demographic and clinical characteristics between the manual and automated screen periods will be examined using bivariate statistics. We will also perform descriptive analysis to examine the proportion of hospitalized patients with substance misuse who received any component of the composite outcome (naloxone dispensing, medication-assisted treatment, addiction consult, referral to outpatient treatment, brief intervention/motivational interviewing for substance misuse) within each month of the study period, and we will plot these proportions using mixed-effects logistic regression, with time (month of observation) modeled using restricted cubic splines. The primary analysis for aim 1 will consist of an interrupted time series approach utilizing autoregressive integrated moving average (ARIMA) models to determine the effect of the automated screener to the manual screen for this outcome. ARIMA models are preferable to alternatives such as segmented regression which may inadequately control for seasonality and autocorrelation in time series data. We will also perform sensitivity analyses to confirm the results of aim 1 using generalized linear mixed-effects models (GLMM) that include random intercepts to account for multiple index encounters over the follow-up time period and adjust for important patient demographics and clinical characteristics including: age, sex, race/ethnicity, insurance status, diagnosis, and comorbidities. GLMMs will also be used to analyze secondary endpoints.

Specific aim 1: First, we will plot the counts of hospitalized patients who received any component of the composite outcome to examine seasonality, trends, and outlying values. A transformation will be applied to stabilize the variance over time if data are heteroscedastic. Differencing will be applied to induce stationarity, such as a difference to account for linear trend ($d=1$, degree of non-seasonal differencing) and autocorrelation functions (ACF) will be plotted to verify stationarity. After differencing,

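### Specific aim 1 lets fit statistics choose the form of the intervention effect on the 24 counts that also supply the test, and names no contrast to set against the non-inferiority margin

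*Combined protocol and SAP*

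**What the plan says.** Specific aim 1 analyses the monthly number of patients with any composite component by an ARIMA interrupted time series. Its hypothesis reads: "We hypothesize that the intervention will promote a step change (binary indicator for a level shift when intervention begins) and possibly a ramp effect". Two sentences of Specific aim 1 decide the model:

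- Fit statistics and residual checks are to identify "a parsimonious and appropriate model based on AR/MA orders, differencing assumptions, and parameters for intervention impact (step, pulse, or ramp"). The effect form stands in the same list as the noise structure, and a pulse, which the hypothesis does not mention, is added.
- On scale: "A transformation will be applied to stabilize the variance over time if data are heteroscedastic".

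The Overview under Methods and Material is broader: "Our analysis will model the trend in the outcome before the implementation of the automated screen", together with the change attributed to the screen and "the difference between the slopes in the pre-period versus post-period". None of these is called primary.

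The Power analysis simulates step effects only: "We propose that a non-inferiority margin of 15 consults is acceptable and a step effect of 20 is a feasible goal". It gives 80% power for a step of +20, from 95 ± 10 consults per month with AR(1) phi 0.4. The plan states no alpha, no confidence-limit rule, and nothing on what follows if a ramp or pulse model is selected.

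**The concern.** Choosing AR and MA orders from the data is ordinary ARIMA practice. Choosing the effect parameter that way is different, for two reasons.

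First, the best-fitting of several effect forms is partly the one that chance favours. A nominal 5% test of its coefficient is no longer a 5% test.

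Second, the three coefficients are different quantities. A step is in counts per month, a ramp is in counts per month per month, and a pulse is a short-lived jump. A margin of 15 stated for a step has no defined meaning for the other two. A data-driven transformation can also move the step off the count scale.

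The study hypothesis is non-inferiority to manual screening. If the selected model has no agreed comparison with the margin, that comparison must be devised after the results are known.

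**Working it through.** **Inputs from the documents.** 12 manual-screen and 12 automated-screen months, so 24 points; mean 95, SD 10, phi 0.4; margin 15; step +20.

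**Assumptions.** SD 10 is the marginal SD; errors are normal AR(1); two-sided 5%; the pulse is the first post-period month; the ramp is coded 1 to 12.

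**The plan's 80%.** It can be neither reproduced nor refuted, because alpha, sidedness, the fitted model and the meaning of ± 10 are not given. With known variance, SE(step) is the square root of the step's diagonal element of 10² × (X'R⁻¹X)⁻¹, where R has entries 0.4^|i−j|. Power against zero is Φ(20/SE − 1.96):

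- Intercept and step: SE 5.60; 20/5.60 − 1.96 = 1.61; power 95%.
- Intercept, linear trend and step: SE 9.44; 20/9.44 − 1.96 = 0.16; power 56%.

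So the stated power depends on terms that the plan leaves open.

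**Scale.** The mean of a ramp coded 1 to 12 is 78/12 = 6.5. A ramp that averages +20 over the post-period has coefficient 20/6.5 = 3.1, and in a step+ramp model its step is about 0. A ramp that averages a loss of 15 has coefficient −15/6.5 = −2.3. A first-month pulse of −15 averages −15/12 = −1.25 over the year. None of these can be read directly against 15.

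**Selection.** AR(1) series of 24 months were simulated and the best-fitting form was taken. Phi and variance were treated as known for the null-error rows, to separate selection from small-sample error. The last two rows pool runs with known and with estimated phi; their lower ends also admit step+ramp as a candidate.

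| Quantity | No trend term | Linear trend term |
|---|---|---|
| Null error, step fixed in advance | 5% | 5% |
| Null error, step, pulse or ramp chosen by fit | 12.2-12.5% | 13.3-13.4% |
| Null error, step+ramp also allowed | 15.2% | 13.4% |
| Ramp-only or pulse-only selected, true step −15 | 21-24% | 30-38% |
| Ramp-only or pulse-only selected, true step +20 | 10-14% | 18-25% |

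With estimated phi but each form calibrated to 5%, selection among the three single forms gives about 13% and 14%, in agreement with the table.

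**Sensitivity (three single forms).**

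- Phi 0.2 to 0.6: a ramp or pulse is selected at −15 in 19-26% (no trend) and 33-38% (trend).
- First differencing, d = 1: 36-38% at −15 and 25-27% at +20. Null error rises from 5.7-6.5% with the step fixed to 12.4-12.6% when step+ramp is also a candidate.
- SD 10 and phi describe consults; the composite's values are not given. If its SD were 15 or 20, a ramp or pulse would be selected at −15 in 40% or 49% (no trend) and 50% or 56% (trend).

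**Narrower reading.** Suppose the step is always kept and fit decides only whether to add a ramp. With calibrated limits at one-sided 2.5%, a true loss of 15 is declared non-inferior in about 4% of studies without a trend term and 2.5% with one.

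**The case against.** The best defence is that the step is the intended effect. It is hypothesised first and it is the only form in the Power analysis. On that reading fit statistics merely decide whether a ramp joins it, and the harm to the non-inferiority conclusion is slight: no inflation with a trend term and about 4% against 2.5% without one. This stands as far as it goes. But the selection sentence does not say that the step is retained, and it adds a pulse that nobody hypothesised.

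It is also fair to say that a contest between single forms leaves out step+ramp, which is closest to what the Overview describes. Admitting it lowers the share of ramp-only and pulse-only selections, and the lower ends of the ranges allow for this. The share remains material.

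A ramp or pulse could indeed be converted to a mean monthly difference. The plan does not say so, and other conversions are possible.

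A reader might infer more than the documents support:

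- *That the false-positive rate is 30-40%.* Simulations with phi estimated by maximum likelihood and normal critical values give about 30% without a trend and 39-40% with one. But a step fixed in advance already gives about 16% there, and residual-df variances with t limits give 24% and 30%. The plan specifies neither method, and much of the excess is small-sample error.
- *That false non-inferiority is greatly inflated.* The plan gives no rule for a selected ramp or pulse, so any such figure rests on a rule supplied by the reader. Under the narrower reading with uncalibrated limits the rate is 10-12%. Without any selection it is 8% for a fixed step and 9.4-10.6% for a fixed step+ramp.
- *That the stated 80% power is wrong.* The inputs needed to judge it are missing.

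**Conclusion.** The point holds. As written, the effect form is selected on the data that test it, while margin and power exist for a step only and no primary contrast is named. Selection alone takes a two-sided 5% null error to about 12-15%. At a true loss equal to the margin, roughly a fifth to a quarter of studies without a trend term, and 30-38% with one, would end with a model that has no pre-stated comparison with the margin. At the planned +20 the shares are about 10-14% and 18-25%.

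The null-error figure concerns a test against zero; the consequence for non-inferiority is the missing comparison. That the rule is open to selection and names no contrast is clear from the text. The percentages are less certain: they rest on consult-based SD and phi, an assumed alpha, AR(1) errors and the listed candidate forms. The plan should be changed, and the change is cheap.

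Two neighbouring matters are separate points and are not counted here: the margin is stated in consults while aim 1 analyses the composite count, and 24 points need small-sample-calibrated limits.

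**What to change.** In Specific aim 1:

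1. Take the effect form out of what fit statistics may choose.
2. Before post-period counts are seen, name one confirmatory contrast on the untransformed count scale. Use either the step coefficient in a model with the linear pre-period trend or, if the Overview's slope change is kept, the mean post-period difference from the projected pre-period trend.
3. Reconcile that model with the Overview, which commits to both the pre-period trend and the slope difference. If either is dropped, amend the Overview and give the reason.
4. State alpha, and the rule that non-inferiority needs the lower confidence limit of the named contrast to lie above minus the margin.
5. Choose AR/MA order and differencing by a rule that does not depend on the effect estimate, for example from pre-period data or with the effect terms fixed.
6. Report other effect forms and transformed-scale models as labelled sensitivity analyses.
7. Re-run and restate power for the named model.

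**Cost.** SAP wording and one simulation. A gradual or short-lived effect may be described mainly in sensitivity analyses. Stated power may fall: with calibrated limits at phi 0.4 and the consult figures, power for +20 against zero is about 78% without a trend and 45% with one. Power for non-inferiority at a true +20 is 98% and 89%; at a true zero effect it is 55% and 28%. The mean-difference contrast extrapolates a trend fitted to 12 months. Its power was not computed here and should be known before it is chosen.
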